3.2 Secondary objectives

1. To estimate the approximate prevalence of MPX in PLWHIV and PrEP users in this retrospective cohort
2. To describe clinical manifestation of MPX and response to MPX treatment in PLWHIV and PrEP users
3. To describe the co-morbidities in PLWHIV and PrEP users

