3.4 Secondary endpoints/outcomes

- Number of MPX patients attending as a percentage of total number of patients the sites have seen over a set period of time (from first Mpoxy patient to last Mpoxy patient**)
- Length of stay in hospital*** for inpatients treated for MPX.
- Time to lesion resolution (if known)
- Differences in the clinical manifestation of MPX in PLWHIV and PrEP users by co-morbidities.

*Hospitalisations for clinical reasons only (i.e. not for precautionary measures or quarantine).

** This is regardless of if these first and last patients were included in the collected data

***in case of multiple hospitalisations, this will be the sum of the length of all stays.

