5.1 Inclusion Criteria

- Diagnosis of MPX was more than 90 days prior to data collection
- Confirmed MPX infection by documented PCR testing on skin and/or mucosal and/or any anatomical site between 1st May 2022 to 1st December 2023
- At least 18 years of age
- Cases (PLWHIV + MPX)
 - Documented HIV-1 infection
- Cases (PrEP users + MPX)
 - Attended a clinic to receive PrEP or self-procured PrEP at time of Mpox diagnosis.

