7.5 Secondary outcome analysis

All secondary outcome analysis will be performed on PLWHIV with MPX compared to PrEP users with MPX.

The prevalence of MPX per site during the study period will be estimated by the number of MPX patients attending the site divided by the total number of patients the sites saw during the study period. The 95%

Confidence Interval of the prevalence will be calculated with the exact Clopper-Pearson method. Fisher exact test will be used to compare the prevalence of MPX in HIV-infected individuals to that of PrEP users.

The length of stay in hospital will be estimated using competing risk models with death as a competing event. Gray's test will be used to compare the duration of hospitalisation between PLWHIV and PrEP users. Unadjusted and adjusted sub-distribution hazard ratios (sHR) will be calculated using competing risk models with death as a competing event. The duration of hospitalization will be defined by the time (days) from hospitalization to hospital discharge or last observation. Adjustment variables will include: Age (<30 vs 30-40 vs >40 years); Sex at birth (female vs male); Comorbidities; multiple sexual partners (yes vs no); number of sexual partners in the last 3 months prior to mpox diagnosis; and Orthopoxvirus vaccination history (yes vs no).

Subgroup analyses for clinical manifestation in MPX will be conducted to assess the difference between PLWHIV and PrEP users across comorbidities. The following comorbidities will be assessed: diabetes mellitus, immunosuppression (e.g. solid organ transplant), chronic kidney or liver disease, mental health illness. Adjusted odds ratio will be calculated to compare PLWHIV and PrEP users within subgroup using logistic regression models. Adjustment variables will include: Age (<30 vs 30-40 vs >40 years); Sex at birth (female vs male); multiple sexual partners (yes vs no); number of sexual partners in the last 3 months prior to mpox diagnosis; and smallpox vaccination history (yes vs no).

Heterogeneity in the impact of HIV infection on clinical manifestations based on comorbidities will be assessed by including terms for interactions between patient status (PLWH and PrEP users) and the comorbidity variable in multivariable logistic regression models. All variables described above for adjustments will be included in the multivariable models.

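### The PLWHIV versus PrEP prevalence comparison has no group-specific denominators and no site term, so secondary objective 1 is not answered by the formula as written

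*Combined protocol and SAP*

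**What the plan says.** - **Objective (3.2 and synopsis).** "To estimate the approximate prevalence of MPX in PLWHIV and PrEP users in this retrospective cohort". The target is a prevalence in each of two groups.
- **Endpoint (3.4 and synopsis).** "Number of MPX patients attending as a percentage of total number of patients the sites have seen over a set period of time". The denominator is everyone seen, with no split by HIV status or PrEP use. The window is "from first Mpoxy patient to last Mpoxy patient"; the synopsis makes clear that this is at the site.
- **Analysis (7.5).** The figure is defined at site level. Its numerator is the count of mpox attenders, which is "divided by the total number of patients the sites saw during the study period". It is to carry an exact Clopper-Pearson 95% interval, and then "Fisher exact test will be used to compare the prevalence of MPX in HIV-infected individuals to that of PrEP users". No stratification, adjustment or rule for combining sites is given for that test.
- **Population for secondary analyses (opening of 7.5).** "All secondary outcome analysis will be performed on PLWHIV with MPX compared to PrEP users with MPX".
- **Data list (6.2).** It covers patients with mpox, with extra items for those with HIV. It contains no clinic-level counts.

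**The concern.** A comparison of two group prevalences needs four numbers per site: cases and patients seen, in each group. The plan defines neither group's number of patients seen. The formula it does give yields the share of all attenders who had mpox, which is not the prevalence in either group. The cases-only rule makes this worse, because a data set of cases contains no non-cases.

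There are two consequences. First, an analyst who applies the one stated denominator to both groups gets a comparison driven partly by how many PLWHIV and PrEP users the clinics look after. Second, an analyst who finds group denominators elsewhere still has a test that ignores site. Up to 12 sites in up to 7 countries are planned, and mpox frequency and the PLWHIV:PrEP mix could both differ between them.

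**Working it through.** The documents state no prevalence, effect size, alpha or power for this comparison, so there is no planned figure to reproduce. The checks below are illustrations.

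**Inputs from 6.1.** 907 PLWHIV with mpox among an estimated 85,279 PLWHIV in care at 31 dashboard sites; 27,416 PrEP users at 45 sites. The site sets differ. No mpox count for PrEP users is given.

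**Assumption.** Equal risk in both groups, set at 907/85,279 = 1.06%. The PrEP case count is then 0.010636 × 27,416 ≈ 292.

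**Check 1: one common denominator T for both groups.** Let r be the risk and N the group size.

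ratio = (r_H·N_H/T) / (r_P·N_P/T) = (r_H/r_P) × (N_H/N_P)

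T cancels, so adding other clinic patients to the denominator does not change the ratio.

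- T = 85,279 + 27,416 = 112,695.
- PLWHIV: 907/112,695 = 0.80%. PrEP: 292/112,695 = 0.26%.
- Ratio 907/292 = 3.11, which is the group-size ratio 85,279/27,416 = 3.11. The true ratio is 1. Fisher P is about 5 × 10⁻⁷⁴.
- Using each group's own denominator: 1.06% (95% CI 1.00 to 1.13%) against 292/27,416 = 1.07%, P = 0.97.
- With per-site averages: 85,279/31 = 2,751 and 27,416/45 = 609, a ratio of 4.5.
- The direction depends on the mix. At an assumed clinic with 1,000 PLWHIV and 3,000 PrEP users, the expected cases are 11 and 32, a ratio of 0.34. With 1,500 of each, the ratio is 1.0.
- A real difference can be reversed. If PrEP users had twice the risk (583 cases), the PrEP:PLWHIV ratio would appear as 583/907 = 0.64 instead of 2.0.

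**Check 2: group denominators, no stratification.** Two assumed sites, with equal risk in both groups within each site:

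| Site | Risk | PLWHIV cases/seen | PrEP cases/seen |
|---|---|---|---|
| A | 1% | 30/3,000 | 10/1,000 |
| B | 4% | 40/1,000 | 120/3,000 |
| Combined | | 70/4,000 = 1.75% | 130/4,000 = 3.25% |

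- Crude OR = (70 × 3,870)/(130 × 3,930) = 0.53, Fisher P = 0.00002.
- Mantel-Haenszel OR = (30×990/4,000 + 40×2,880/4,000) / (10×2,970/4,000 + 120×960/4,000) = 36.225/36.225 = 1.00.
- With 2% instead of 4% at site B, the crude OR is 0.71 (P = 0.08).
- With the same mix at both sites (3,000 and 1,000 each; risks 2% and 4%), the crude OR is 1.00. Both mix and mpox frequency must vary for site to confound.

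**Check 3: the cases-only rule.** Applied literally, every analysed person in both groups has mpox, so each group's prevalence would be 100% and there would be nothing to compare.

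**The case against.** A reader might infer that the planned comparison definitely measures clinic mix instead of mpox risk, or that it is certain to reject when risks are equal. The documents do not support that. Section 7.5 attaches the all-patients denominator to the prevalence per site. The Fisher sentence is separate, and its ordinary meaning is cases among HIV-infected patients against cases among PrEP users. A shared denominator would put the same people in both rows of the table, which is an unlikely intention. That the test pools sites is likewise inferred from silence.

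The absence of group counts from 6.2 does not prove that they will not be obtained. That list is patient-level and omits the total number of patients seen too, although the endpoint plainly needs it. The figures in 6.1 show that the network has gathered group counts before.

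The illustrations are also constructed. Applying the per-site averages to 12 sites at equal risk gives about 351 + 78 = 429 cases, against roughly 2,000 planned, so they do not describe the intended sites. No site-level data are given to show how far mix or mpox frequency varies.

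All of this stands, and it limits how strongly the numbers can be read. It does not supply the missing definition. Even on the favourable reading, the plan states no group denominators and does not provide for collecting them. It also states no handling of site, and its cases-only rule conflicts with any prevalence.

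**Conclusion.** The point holds as a gap between objective and formula. The stated endpoint does not give the prevalence in either group, and the stated comparison lacks both its denominators and a site term. This part needs no assumption.

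The size of any distortion is conditional. On the common-denominator reading it equals the group-size ratio: about 3.1 from the network totals or 4.5 from per-site averages, assuming equal risk and combining different site sets. With group denominators it depends on site variation that the documents do not report; the odds ratio of 0.53 against 1.00 comes from invented sites with a reversed mix and a fourfold risk difference.

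The impact is limited. The objective is secondary and described as approximate, the study is mainly descriptive, and no primary endpoint depends on it. The plan should still be changed, because the remedy is cheap and the objective cannot be met from the current text.

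**What to change.** 1. In 3.4 and 7.5, define prevalence for each group as mpox cases of that group attending, divided by unique patients of that group seen.
2. Use one window. The interval in 3.4 ("from first Mpoxy patient to last Mpoxy patient") and the study period in 7.5 must be reconciled with each other and with the diagnosis dates in 5.1 ("between 1st May 2022 to 1st December 2023").
3. Collect from each site, as aggregates, the unique PLWHIV seen, the unique PrEP users seen and all mpox cases in each group, whether or not entered in the eCRF. Say how self-procured PrEP users, who are eligible under 5.1, are counted in the denominator.
4. State that this analysis is exempt from the cases-only restriction at the start of 7.5.
5. Keep the Clopper-Pearson intervals. Replace the unstratified Fisher test with a Cochran-Mantel-Haenszel or exact test stratified by site.

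The cost is three or four aggregate counts per site, at most 4 × 12 = 48 numbers, plus SAP wording. No further patient-level data are needed.

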7.4 Primary outcome analysis

The first primary outcome analysis will be to describe outcomes of MPX in PLWHIV and in PrEP users in terms of severity of lesions, time to lesion resolution, hospitalization, death.

The rate of serious lesions will be estimated by dividing the number of participants with serious lesions by the total number of participants in the full analysis population. Unadjusted and adjusted odds ratios (ORs) will be calculated using the logistic regression model to assess the impact of HIV on the occurrence of serious lesions compared to PrEP users.

Because some participants' lesion may not be healed by the end of the study period and, therefore, the duration of resolution would not be known, and thus right-censored, survival analysis methods such as the Kaplan-Meier and Cox model will be used to assess the time to lesion resolution. Kaplan-Meier estimates will be used to estimate the median time to lesion resolution. Unadjusted and adjusted hazard ratios (HR) will be estimated using the Cox proportional hazard model to assess the impact of HIV-infection on the time to lesion resolution compared with PrEP users.

The hospitalization rate will be estimated by dividing the number of participants hospitalized for mpox infection by the total number of participants in the total analysis population. Unadjusted and adjusted odds ratios (ORs) will be calculated using the logistic regression model to compare hospitalization rates between PLWHIV and PrEP users.

The mortality rate will be estimated using the Kaplan-Meier Method. Unadjusted and adjusted hazard ratios (HR) will be calculated using the Cox proportional hazard model to compare the rates of mortality between PLWHIV and PrEP users.

Adjustment variables will include the following potential confounders: Age (<30 vs 30-40 vs >40 years); Sex at birth (female vs male); Comorbidities; multiple sexual partners (yes vs no); number of sexual partners in the last 3 months prior to mpox diagnosis; and smallpox vaccination history (yes vs no).

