The second primary outcome analysis will be performed between PLWHIV with MPX versus PrEP users with MPX. The endpoint is to assess differences in clinical manifestations of MPX between the groups. Unadjusted and adjusted odds ratios (ORs) will be calculated using the logistic regression models to compare the rates of clinical manifestations between PLWHIH and PrEP users. The adjusted variables will be the following (potential confounders): Age (<30 vs 30-40 vs >40 years); Sex at birth (female vs male); Comorbidities; multiple sexual partners (yes vs no); number of sexual partners in the last 3 months prior to MPX diagnosis; and smallpox vaccination history (yes vs no).

The third primary outcome analysis will be performed within the PLWHIV group. The endpoint is to evaluate the characteristics of HIV infection associated with severe mpox. Univariable and multivariable logistic regression models will be used to assess factors associated with severe mpox in PLWHIV. The following variables will be evaluated: time since HIV diagnosis (years); current ART; CDC disease stage; CD4 cell nadir; last CD4 cell count/HIV-RNA before MPX diagnosis (including CD4% and CD4/CD8 ratio). Variables achieving $P < 0.20$ in the univariable analysis will be retained for the multivariable analysis.

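### The section 7.5 comorbidity subgroup models leave the other comorbidities out of the adjustment list, although section 7.4 adjusts for them for the same outcome and contrast

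*Combined protocol and SAP*

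**What the plan says.** The plan has four adjustment lists for comparisons of PLWHIV with PrEP users. Three of them name comorbidities:

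- Section 7.4, first primary analysis: "Adjustment variables will include the following potential confounders: Age (<30 vs 30-40 vs >40 years); Sex at birth (female vs male); Comorbidities".
- Section 7.4, second primary analysis (clinical manifestations): "The adjusted variables will be the following (potential confounders): Age (<30 vs 30-40 vs >40 years); Sex at birth (female vs male); Comorbidities".
- Section 7.5, length of hospital stay: "Sex at birth (female vs male); Comorbidities; multiple sexual partners (yes vs no); number of sexual partners in the last 3 months prior to mpox".

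The fourth list, for the comorbidity subgroups in section 7.5, does not: "Adjustment variables will include: Age (<30 vs 30-40 vs >40 years); Sex at birth (female vs male); multiple sexual partners (yes vs no"), followed by number of recent partners and smallpox vaccination.

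The subgroup conditions are set out in the same paragraph: "The following comorbidities will be assessed: diabetes mellitus, immunosuppression (e.g. solid organ transplant), chronic kidney or liver disease, mental health illness". The estimate wanted is a stratum-specific one: "Adjusted odds ratio will be calculated to compare PLWHIV and PrEP users within subgroup using logistic regression models".

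The section then describes a test of heterogeneity. It uses a multivariable logistic model with an interaction between patient status and the comorbidity variable, and adds: "All variables described above for adjustments will be included in the multivariable models".

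**The concern.** The second primary analysis and the subgroup analysis share an outcome (clinical manifestations), a contrast (PLWHIV v PrEP users) and a model (logistic regression). The plan treats comorbidities as potential confounders in the first and removes the whole item in the second, without giving a reason. The natural reason is that the subgroup is itself defined by a comorbidity, but that accounts for removing only that one condition. Section 7.5 lists four conditions, and a patient can have several.

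Read as written, the HIV odds ratio among people with diabetes is not adjusted for the other three conditions. Nor is the odds ratio among people without diabetes, some of whom have those conditions.

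Differences in manifestations by comorbidity form a named secondary endpoint (section 3.4), and this is the planned analysis for it. Two things are at stake. A subgroup odds ratio could carry part of the effect of another condition. And readers will set the subgroup odds ratios beside the overall adjusted odds ratio of 7.4, where a difference could come from the change of adjustment set rather than from heterogeneity.

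**Working it through.** **Comparison of the lists**

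| Analysis | Age, sex, partners, vaccination | Comorbidities |
|---|---|---|
| 7.4, severity of lesions, resolution, hospitalisation, death | yes | yes |
| 7.4, clinical manifestations | yes | yes |
| 7.5, length of stay | yes | yes |
| 7.5, clinical manifestations within comorbidity subgroups | yes | **not listed** |
| 7.5, HIV-by-comorbidity interaction | yes | index condition yes; others unclear |

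The last row is unclear because the sentence that brings in the variables described above does not say which list it means. If it means the subgroup list just before it, the non-index conditions are out. If it means every list above, they are in, and the interaction model then has a different adjustment set from the subgroup odds ratios whose heterogeneity it tests.

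**Size of the possible bias**

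The plan states no figure to reproduce. It gives no comorbidity prevalences and no association between comorbidity and manifestation, so every input below is an assumption.

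- True HIV odds ratio: 1.
- Risk of the manifestation without the omitted condition, p0: 10% or 30%.
- Odds ratio of the omitted condition for the manifestation, R: 1.5, 2 or 3.
- Prevalence q of the omitted condition within the index stratum, PLWHIV v PrEP users: 35% v 15%, or 40% v 25%. In the stratum without the index condition: 15% v 10%.

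Formulas: odds with the condition = R × p0/(1 − p0), which gives p1. Risk in a group = (1 − q) × p0 + q × p1. The apparent HIV odds ratio is the ratio of the two groups' odds.

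Worked case, p0 = 10%, R = 2, 35% v 15%:

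- Odds with the condition = 2 × 0.1/0.9 = 0.222, so p1 = 0.182.
- PLWHIV: 0.65 × 0.10 + 0.35 × 0.182 = 0.1286.
- PrEP users: 0.85 × 0.10 + 0.15 × 0.182 = 0.1123.
- Apparent odds ratio: (0.1286/0.8714) / (0.1123/0.8877) = 1.17, where the truth is 1.

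Apparent odds ratio in the index stratum:

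| Imbalance | R = 1.5 | R = 2 | R = 3 |
|---|---|---|---|
| Equal in both groups | 1.00 | 1.00 | 1.00 |
| 40% v 25% | 1.06–1.07 | 1.11–1.12 | 1.18–1.20 |
| 35% v 15% | 1.09 | 1.16–1.17 | 1.25–1.29 |

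Ranges run over p0 = 10% and 30%. If PrEP users had more of the omitted condition, the shift would go the other way.

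If the interaction model also left the other conditions out, the spurious ratio of odds ratios would be the index-stratum value divided by the value at 15% v 10%. In the worked case that is 1.167/1.043 = 1.12. Over all these cases it is 1.04 to 1.20. It is 1.00 if the imbalance is the same in both strata.

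**Set against precision**

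Assume equal HIV groups and a subgroup of 100 people. The standard error of the log odds ratio is √[2 / (50 × p(1 − p))].

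- p = 10%: √(2/4.5) = 0.667; the 95% interval extends by a factor of exp(1.96 × 0.667) = 3.69 either way.
- p = 30%: √(2/10.5) = 0.436; factor 2.35.

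For the interaction ratio with 2000 people and the index condition in 3% to 10% of them (assumed; 60 to 200 people), adding the variances of the two strata gives factors from 1.89 (10% prevalence, p = 30%) to 5.54 (3% prevalence, p = 10%).

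**The case against.** **The interaction model.** A reader might infer that the interaction models also drop every comorbidity. The text does not support that. The index condition is in the model through its interaction with patient status, and the reference to all variables described above can be read to bring comorbidities back in from the earlier lists. What stands for that model is an ambiguity, and the spurious-interaction figures apply only under the less favourable reading.

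**Confounding.** A reader might also infer that the subgroup odds ratios are confounded. The plan speaks of potential confounders, and bias needs another condition that both differs by HIV status within the stratum and affects the manifestation. The documents give data on neither.

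**Coding.** Section 7.4 gives levels for age, sex, multiple partners and vaccination but none for comorbidities. If comorbidity were a single any/none variable, it would be constant among people with diabetes and would have to leave that stratum's model. This is fair, but it would still vary among people without diabetes, and section 7.5 itself treats the conditions one by one. The fix should therefore specify separate indicators.

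**Sparse strata.** The subgroup models are fitted within subgroups, where extra terms for uncommon conditions can cause separation. A short list there is a defensible trade-off, although the plan does not give that reason. This point stands and shapes the fix.

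**Open wording.** The phrase introducing the list is not explicitly exhaustive. That is a weak defence: the same phrase introduces the length-of-stay list in the same section, which names comorbidities.

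**Consequence.** This is one secondary endpoint in a study that section 7.2 calls primarily descriptive, and the primary comparison of manifestations does adjust for comorbidities. This stands and limits the weight of the point.

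**Conclusion.** The subgroup models of section 7.5, as written, omit the non-index comorbidities that section 7.4 treats as potential confounders for the same outcome and contrast. The within-stratum HIV odds ratios may therefore be confounded, and they do not share an adjustment set with the overall odds ratio of 7.4. For the interaction model the fault is only that its covariates are not clear.

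The size of any bias cannot be known from the documents. It is nil under balance. Under the assumed imbalances and odds ratios of 1.5 to 3 for the omitted condition, a true odds ratio of 1 would appear as about 1.06 to 1.29. In a stratum of about 100 people that lies well inside the sampling error. The primary analyses are unaffected. The change is worth making because it is cheap and because the plan already accepts the reason for it in 7.4.

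**What to change.** In section 7.5, state three things:

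- The interaction model for each comorbidity is fitted in the full population. It contains HIV status, the index comorbidity, their interaction, the listed demographic, partner and vaccination variables, and the other listed comorbidities as main effects, each as a separate indicator.
- The stratum-specific HIV odds ratios are taken from that model, not from separate fits in small strata.
- The closing sentence on adjustment variables refers to this list.

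No new data are needed: section 6.2 already collects diabetes, other immunosuppression, chronic kidney or liver disease and mental health conditions, where routinely available.

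The cost is three extra parameters (four conditions less the index one), or four if kidney and liver disease are coded separately, in a model for about 2000 people. Taking the stratum estimates from one model also assumes that the other covariates have the same effect in people with and without the index condition. The plan should say so.
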